**FRED HUTCHINSON CANCER RESEARCH CENTER
UNIVERSITY OF WASHINGTON SCHOOL OF MEDICINE**

**Personalized radiation therapy through functional lung avoidance and
response-adaptive dose escalation: utilizing multimodal molecular
imaging to improve the therapeutic ratio (FLARE RT)**

Principal Investigator: [name]
Associate Professor
Department of Radiation Oncology
University of Washington Medical Center
[name]
[name]
[contact]
[contact]
Email: [contact]

Co-Investigators: [name]
[name]
[name], PhD
[name]

Version date:

Protocol Amendment 4: version February 5, 2020

Study Summary

Title	Personalized radiation therapy through response-adaptive dose escalation and functional lung avoidance: utilizing multimodal molecular imaging to improve the therapeutic ratio (FLARE RT)
Short Title	FLARE RT
Protocol Number	CCIRB 9599
Phase	Phase II
Methodology	Single Arm Open-Label
Study Duration	5 yrs.
Study Center(s)	University of Washington Medical Center
Objectives	To utilize mid-treatment FDG PET/CT tumor response to select non-responding patients for dose escalation, while utilizing functional lung avoidance to mitigate toxicity. Changes in tumor FDG uptake on mid-treatment PET/CT (24 Gy nominal) will divide patients into “responders” and “non-responders”. Responders will receive 60 Gy to their tumor per standard of care; non-responders will undergo dose escalation to 74 Gy. All patients will receive functional lung avoidance radiation treatment via SPECT/CT imaging with ^{99m}Tc-MAA and ^{99m}Tc-SULFUR COLLOID to accurately identify and preferentially spare functional lung. Primary endpoint of this study will be 2-yr. overall survival.
Number of Subjects	The projected enrollment number is 60 in order to meet the study goal of 50 evaluable subjects.
Diagnosis and Main Inclusion Criteria	Patients diagnosed with stage IIB-III non-small cell lung cancer receiving definitive chemoradiation.
Study Product, Dose, Route, Regimen	All scans are FDA approved for use with patients: ^{18}FFDG-PET/CT and SPECT/CT with ^{99m}Tc-MAA and ^{99m}Tc-Sulfur Colloid
Duration of administration	Beyond standard of care imaging, some patients may undergo a repeat baseline protocol specific FDG-PET/CT, and be considered research, then a PET/CT mid-treatment, and 2 SPECT/CT scans (pre-treatment and 3 months post-treatment).

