1.5 Radiation to the Lungs Causes Pulmonary Toxicity and Limits the Deliverable Dose

When improving the therapeutic ratio, dose escalation must always be weighed against potentially increased toxicity. Radiation to the lungs cause a spectrum of changes, with the two most clinically relevant changes being radiation pneumonitis (RP) and radiation induced fibrosis. Radiation pneumonitis is a disorder characterized by inflammation focally or diffusely affecting the lung parenchyma. It occurs in the subacute phase after radiation treatment, from several weeks to several months after completion of therapy. Radiation pneumonitis can be mild, causing shortness of breath that does not require intervention and resolves spontaneously, to severe, requiring steroids, oxygen, ventilation, or, if not treatable even, even death. Radiation pneumonitis is a dose-limiting toxicity in lung cancer treatment, causing worsening respiration in patients who often already have underlying lung disease, such as emphysema. Approximately 15-40% of patients develop clinically significant radiation pneumonitis after treatment with conventional radiation doses (25). Long term, lung tissue treated with radiation can develop fibrosis, and is no longer able to function in gas-exchange. This can lead to a permanent reduction in pulmonary function. Symptomatic lung damage is the major impediment to safely escalate dose to lung tumors.

1.6 Current Radiation Planning Methods are Unable to Accurately Predict Which Patients Will Develop Pulmonary Toxicity

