The primary endpoint of the study will be 2 year overall survival. The primary objective will be to test the superiority of 2yr OS in the FLARE RT patient cohort over the 60 Gy cohort of RTOG 0617 (57% 2yr OS) for historical control. Based on an estimated improvement to 72% 2yr OS, we will enroll at least **49 patients** to test for superiority of FLARE RT at 80% power and 5% Type I error.

Secondary Objective

[figure not shown]
- CTCAE v4 grade 2 or higher pneumonitis incidence from FLARE RT compared to historical controls (non-inferiority test)
- 1 yr local control, progression-free survival, and pulmonary function test decline
- Identification of baseline FDG PET/CT and mid-treatment FDG PET/CT imaging biomarkers for predicting patient survival
- Identification of baseline perfusion SPECT/CT imaging biomarkers for predicting G2+ pneumonitis and PFT decline
- Collection of plasma and urine samples for future correlative studies between imaging biomarkers and cytokine biomarkers of radiation response in both tumor and normal tissue

3 Study Design

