Secondary objectives will feature a non-inferiority proportionality test of pulmonary toxicity incidence, defined as CTCAE v4 grade 2 or higher pneumonitis, between patients receiving FLARE RT and historical rates. Interim and final statistical analyses of the clinical endpoints (local control, progression-free survival, overall survival) will consist of Kaplan-Meier estimation and Cox proportional hazard regression. We will not conduct formal subset analyses due to insufficient statistical power. However, we will assess the relative strengths of hazard ratio estimates (and 95% confidence intervals) from a few predictors, including pre-treatment and mid-treatment imaging metrics extracted from PET/CT and SPECT/CT data. The degree of correlation amongst the variables will be evaluated. We will conduct linear regression of post-treatment lung perfusion SPECT/CT changes and decline in standard pulmonary function tests (FEV1,

DLCO, etc.). Lastly, we will perform ROC analysis to associate pre-treatment lung perfusion SPECT/CT parameters with dichotomous incidence of pneumonitis.

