5.1 Dose Specifications

All patients will undergo treatment planning at initial simulation to 60 Gy at 2.0 Gy per fraction, using perfusion SPECT/CT to guide functional lung avoidance (details below). At 24 Gy (20-30 Gy acceptable), mid-treatment FDG PET/CT will be performed, and changes in tumor SUV and total lesion glycolysis (TLG) will be assessed to divide patients into metabolic responders and metabolic non-responders (details below). Patients classified as metabolic non-responders will receive dose escalation to 74 Gy, completed in 30 fractions (starting fraction 16, there will be hypofractionated dose escalation, dividing the additional 44 Gy into the remaining 15 fractions).

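### Imaging metrics are to be compared on hazard ratio size without a common scale, and perfusion parameters on apparent ROC without correction for choosing among them

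*Combined protocol and SAP*

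**What the plan says.** Section 2 (Study Objectives) has two secondary objectives of this kind: "Identification of baseline FDG PET/CT and mid-treatment FDG PET/CT imaging biomarkers for predicting patient survival" and "Identification of baseline perfusion SPECT/CT imaging biomarkers for predicting G2+ pneumonitis and PFT decline".

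Section 3.2 (Statistical Plan) gives the methods. For the clinical endpoints, analysed by Kaplan-Meier and Cox regression, "we will assess the relative strengths of hazard ratio estimates (and 95% confidence intervals) from a few predictors". Those predictors are described only by their source, with no individual metric named: "including pre-treatment and mid-treatment imaging metrics extracted from PET/CT and SPECT/CT data". For pneumonitis, "we will perform ROC analysis to associate pre-treatment lung perfusion SPECT/CT parameters with dichotomous incidence of pneumonitis".

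Section 3.2 also declines formal subset analyses for lack of power and will examine the correlation among variables. It does not give:

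- the scale of the hazard ratios (per unit, per standard deviation, or dichotomised);
- a list or number of candidate metrics;
- a discrimination measure for survival;
- internal validation, or any allowance for trying several metrics.

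On size, the Study Summary states: "The projected enrollment number is 60 in order to meet the study goal of 50 evaluable subjects". No event count, power or precision is given for the biomarker analyses.

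**The concern.** A hazard ratio from a continuous metric is the change in hazard per unit of that metric. Sections 5.1 and 5.3 bring in metrics with very different natural units: an SUV, and total lesion glycolysis (TLG), which is mean SUV times metabolic volume. SPECT uptake metrics are added to these. If absolute values are entered as measured, the larger hazard ratio may reflect only the smaller-valued unit.

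The ROC analysis has a different weakness, unrelated to units. If several perfusion parameters are tried in about 50 patients and the most promising is carried forward, its apparent AUC is too high on average, because the same patients choose the parameter and score it.

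At stake is which metric goes into later work. Section 1.1 asks whether lung-heterogeneity parameters can pick out patients at highest risk of toxicity before treatment, and says that the answers will support a multi-center trial. A weak or useless metric could be taken forward with an overstated AUC.

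**Working it through.** The plan has no figure of its own to reproduce here. Its 49 patients are sized for the primary survival test. I use the 50 evaluable patients.

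**1. Events available**

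- Pneumonitis: Section 1.5 says "Approximately 15-40% of patients develop clinically significant radiation pneumonitis after treatment with conventional radiation doses". 50 × 0.15 = 7.5 and 50 × 0.40 = 20, so about 7 to 20 cases. This assumes that the background rate carries over to grade 2 or higher pneumonitis under functional lung avoidance.
- Deaths by 2 years, from the survival rates in Section 3.2: 50 × (1 − 0.72) = 14 and 50 × (1 − 0.57) = 21.5, so 14 to 22.

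**2. Hazard ratios and units**

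HR per unit = (HR per SD)^(1/SD). All SDs and HRs here are assumed, for illustration.

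- TLG, HR 1.6 per SD, SD 400: 1.6^(1/400) = 1.0012.
- Absolute SUVmax, HR 1.2 per SD, SD 5: 1.2^(1/5) = 1.037.

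The weaker metric shows the larger hazard ratio per unit.

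A Cox simulation (50 patients, 72% 2-year survival, 500 runs) set a real predictor (HR 2.0 per SD, SD 100) against a useless metric (SD 0.2). Compared on |log HR| per raw unit, the useless metric came first in 99% of runs; compared per SD, in 6%. These scales were chosen to be far apart, so the result shows what the wording allows, not what is expected.

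Rescaling a linear covariate multiplies log HR and its standard error by the same factor. The z statistic, and whether the interval excludes 1, therefore do not change.

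**3. Choosing among useless perfusion parameters**

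For k independent useless parameters each tested at 5%, the chance that at least one is nominally significant is 1 − 0.95^k:

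- k = 3: 14%
- k = 5: 23%
- k = 10: 40%

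Simulation with correlation 0.5 between parameters lowers these to about 12% for k = 3, 18% for k = 5 and 28-29% for k = 10. Over all the runs with 3 to 10 parameters the range is roughly 11-41%, and it depends little on the number of cases.

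The chance that the best apparent AUC (either direction) is at least 0.70, simulated with n = 50, does depend on the number of cases. The lower figure is for correlation 0.5 and the upper for independence:

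| Cases | k = 3 | k = 5 | k = 10 |
|---|---|---|---|
| 8 | 19-21% | 26-33% | 41-54% |
| 10 | 14-16% | 20-24% | 31-42% |
| 15 | 6-8% | 10-12% | 17-22% |
| 20 | 4-5% | 7-8% | 12-16% |

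For one parameter named in advance the chance is about 5% with 10 cases and 3% with 15.

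**4. Precision without any selection**

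- AUC of 0.70 (Hanley-McNeil standard error 0.100 with 10 cases, 0.085 with 15): 0.70 ± 1.96 × 0.100 gives 0.50 to 0.90; 0.70 ± 1.96 × 0.085 gives 0.53 to 0.87.
- HR per SD, 95% interval factor exp(1.96/√deaths): exp(1.96/√14) = 1.69 and exp(1.96/√22) = 1.52.

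**The case against.** The strongest reply is that the plan is silent on these matters and does not commit the error. Much of that stands.

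- **Raw ranking.** A reader might infer that metrics will be ranked on raw hazard ratios and a best one named. Section 3.2 does not say so. Hazard ratios per SD, per interquartile range or dichotomised would all fit its wording. What remains is that comparing strength presupposes a scale, that identifying biomarkers implies some choice, and that the text permits the raw comparison.
- **Confidence intervals.** These are promised, and a careful reader could recover the z statistic from them whatever the unit. That protects in part. It neither puts the hazard ratios on a common scale nor corrects for selection.
- **Percent change.** Section 5.5 classifies response by change in SUVmax and in TLG, each against a nominal 15%. In that form the two share a scale and the unit problem between them disappears. It remains for absolute values and for PET against SPECT metrics.
- **Number of parameters.** The plan gives none for the ROC analysis, and its wording for the Cox predictors suggests a small set. With 3 the AUC inflation is modest, but nominal significance is still more than twice 5%.
- **Inflated AUC.** A reader might conclude that every reported AUC will be too high. That does not follow: a single metric named in advance carries no selection optimism. The plan names none and speaks of parameters in the plural.
- **Scope.** Section 1.1 calls this a pilot, and Section 3.2 acknowledges limited power for subsets. Both temper the consequences, but neither addresses scale or selection.

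**Conclusion.** The point holds as a gap with a cheap remedy. Section 3.2 compares hazard ratio size across metrics without a common scale and uses apparent ROC for several parameters without allowing for the choice among them.

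If the strongest of 3 to 10 useless perfusion parameters were picked, it would be nominally significant in roughly 11-41% of trials instead of 5%. Its AUC would reach 0.70 in about 6-22% of trials with 15 cases and 14-42% with 10.

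These figures rest on 50 evaluable patients, an assumed number of parameters, and correlation between 0 and 0.5. A reader might fix the case count at 10 to 15, which is 20-30% of 50; the documents support only the wider 7 to 20. The size of the unit effect cannot be stated, because the plan gives neither the scale nor the spread of the metrics.

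This is a desirable improvement to secondary analyses. It does not touch the primary endpoint.

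**What to change.** In Section 3.2:

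1. List the candidate PET and SPECT metrics before analysis, stating for each whether the absolute value or the percent change is used.
2. Report each hazard ratio per SD (or per interquartile range) with its 95% confidence interval.
3. Compare metrics on the C-index for overall survival and the AUC for pneumonitis, with confidence intervals. Correct both for optimism by a bootstrap that repeats any step in which a metric or cut-off is chosen.
4. Label the results exploratory.

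Log-transforming TLG and metabolic volume is optional.

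The cost is plan wording and a little more analysis, with no change to patients, visits or scans. Reported values will look less favourable, and the corrected estimates will stay imprecise with 14 to 22 deaths by 2 years and 7 to 20 pneumonitis cases.

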3.3. Eligibility

Conditions for patient eligibility:

- *Pathologically proven (either histologic or cytologic) diagnosis of Stage IIB-IIIB non-small cell lung cancer (NSCLC); according to AJCC Staging, 7th edition.*
 - *Staging workup must include: brain imaging (CT head or MRI brain) and PET/CT.*
 - *Pleural effusions must have cytology to rule out malignant involvement unless too small to undergo thoracentesis per radiology*
- *Patients must be considered unresectable or inoperable*
- *Patient must not have received prior radiation for this lung cancer*
- *Patients must be having concurrent chemotherapy*
- *Nodal recurrences can be treated on this protocol but prior curative surgery for lung cancer must have been at least 6 months prior to the nodal recurrence.*
- *Patients must have measurable or evaluable disease that is FDG avid with SUV>3 on PET/CT*
- *Zubrod Performance Status 0-1;*
- *Age ≥ 18 ;*
- *PFTs including FEV1 within 26 weeks prior to registration; for FEV1, the best value obtained pre- or post-bronchodilator must be ≥ 0.8 liters/second or $\geq 50\%$ predicted.*
- *CBC/differential obtained within 8 weeks prior to registration on study, with adequate bone marrow function defined as follows:*
 - *Absolute neutrophil count (ANC) $\geq 1,800$ cells/mm³;*
 - *Platelets $\geq 100,000$ cells/mm³;*
 - *Hemoglobin ≥ 10.0 g/dl (Note: The use of transfusion or other intervention to achieve Hgb ≥ 10.0 g/dl is acceptable.)*
- *Serum creatinine within normal institutional limits or creatinine clearance ≥ 40 ml/min;*
- *Bilirubin must be within or below normal institutional limits;*
- *AST and ALT $< 2.5 \times$ the IULN;*
- *Patient must sign study specific informed consent prior to study entry.*

Conditions for patient ineligibility:

- *>10% unintentional weight loss within the past month*
- *Prior invasive malignancy (except non-melanomatous skin cancer) unless disease free for a minimum of 3 years; non-invasive conditions such as carcinoma in situ of the breast, oral cavity, or cervix are all permissible.*
- *Prior radiotherapy to the region of the study cancer that would result in overlap of radiation therapy fields;*
- *Pregnancy or women of childbearing potential and men who are sexually active and not willing/able to use medically acceptable forms of contraception.*

4 Study Registration

Subjects will be registered by the FHCRC/UW Study Coordinator and entered into OnCore at seattlectms.org. A complete, signed, study consent and HIPAA consent are required for registration.

5 Radiation Therapy

5.1 Dose Specifications

All patients will undergo treatment planning at initial simulation to 60 Gy at 2.0 Gy per fraction, using perfusion SPECT/CT to guide functional lung avoidance (details below). At 24 Gy (20-30 Gy acceptable), mid-treatment FDG PET/CT will be performed, and changes in tumor SUV and total lesion glycolysis (TLG) will be assessed to divide patients into metabolic responders and metabolic non-responders (details below). Patients classified as metabolic non-responders will receive dose escalation to 74 Gy, completed in 30 fractions (starting fraction 16, there will be hypofractionated dose escalation, dividing the additional 44 Gy into the remaining 15 fractions).

5.2 Localization, simulation, and immobilization

- Volumetric treatment planning CT study will be required to define gross tumor volume (GTV), clinical target volume (CTV), and planning target volume (PTV) (see definitions below). Each patient will be positioned in an immobilization device in the treatment position on a flat table.
- Contiguous CT slices, having 3 mm thickness through the regions harboring gross tumor and grossly enlarged lymph nodes and 8-10 mm thickness of the remaining regions are to be obtained starting from the level of the cricoid cartilage and extending inferiorly through the entire liver volume. The GTV, CTV, and PTV and normal organs will be outlined on all appropriate CT slices.
- A treatment planning FDG PET/CT scan and SPECT/CT scan with the patient in the treatment position is strongly encouraged for treatment planning.
- 4-dimensional radiation treatment planning is required.

5.3 Target Volumes

- Definition of the GTV: The primary tumor and clinically positive lymph nodes seen either on the planning CT (> 1 cm short axis diameter) or pretreatment PET scan ($SUV > 3$) will constitute the GTV.
- The ITV includes the envelope that encompasses the tumor motion for a complete respiratory cycle.
- Definition of the CTV: The CTV is defined to be the ITV plus a 0.5 cm to 1 cm margin as appropriate to account for microscopic tumor extension.
- Definition of the PTV: PTV margin should account for setup uncertainties and may be individualized but should not be less than 0.5 cm with daily imaging guidance.
- Definition of the metabolic tumor volume (MTV): the MTV is defined as the FDG PET avid volume for response assessment of total lesion glycolysis (TLG = $SUV_{mean} * MTV$) between baseline and mid-treatment scans.

5.4 Critical Structures

Anatomic based clinical objectives will be prioritized first in treatment planning, to ensure that functional lung avoidance radiation treatment will be at least as safe as current standard of care (details on functional lung avoidance planning below).

- Definition of perfused lung-CTV: the structure is derived by applying a fixed threshold of 70% of maximum intensity on MAA SPECT/CT (rigidly aligned to the planning CT) within the lung-CTV structure

5.5 Treatment Planning

Following the trial schema, we will deliver functional lung avoidance RT plans that meet pre-treatment functional lung objectives and PTV coverage. The treatment plans will be subsequently adapted to dose escalate after 3 weeks of RT based on a mid-treatment PET/CT (image after 24 Gy, between fraction 12-13 nominal) in select patients classified as FDG non-responders based on change in SUV_{max} (< 15% nominal) and total lesion glycolysis (< 15% nominal) reported from prior patient series with validation against local control and survival (23-24). FLARE RT plans will maintain 60 Gy base dose to the pre-treatment PTV, while delivering a concomitant boost to mid-treatment PTV (defined by 3 week PET/CT) during weeks 4-6 up to a total mean dose of 74 Gy in 30 fx. The 14 Gy mid-treatment PTV boost will be distributed according to relative mid-treatment FDG PET SUV. Patients who are classified as FDG responders (as defined above) at 3 weeks mid-RT will continue receiving functional lung avoidance RT to a total dose of 60 Gy, without plan adaptation.

The FLARE RT plans will be generated from unique FDG PET/CT and perfusion SPECT/CT objectives that redistribute dose at every image voxel away from functional lung regions and towards FDG-avid tumor regions. This combined differential avoidance [38] and differential tumor dose escalation [39-41] is a form of dose painting that creates continuous dose gradients rather than sharp dose gradients, which increases the robustness of FLARE RT to target motion and patient setup-induced uncertainties. In effect, the low spatial resolution PET and SPECT images acquired over many patient respiratory cycles define blurred targets and avoidance regions that help mitigate the effects of motion and risk of geographic miss during delivery of FLARE RT. Mathematically, FLARE RT objectives for FDG PET/CT-based dose escalation levels and MAA perfusion SPECT/CT-based dose avoidance levels are tabulated in the planning system as part of the cost function for plan optimization.

All FLARE RT planning clinical goals are listed in Table 2.

Structure	Clinical Goal	Type	Minor Violation	Major Violation
Pre-treatment PTV	$V_{54\text{Gy}} = 100\%$	Objective	$\geq 95\%$	$< 95\%$
	$V_{60\text{Gy}} > 95\%$	Objective	$\geq 90\%$	$< 90\%$
Mid-treatment PTV	Mean Dose = 74Gy	Objective	$\geq 66\text{Gy}$	$< 66\text{Gy}$
	Min Dose = $60\text{Gy} + 14\text{Gy} \frac{SUV_{\text{min}}^{\text{mid PTV}}}{SUV_{\text{mean}}^{\text{mid PTV}}}$	Recommendation	-	-
	Max Dose = $60\text{Gy} + 14\text{Gy} \frac{SUV_{\text{max}}^{\text{mid PTV}}}{SUV_{\text{mean}}^{\text{mid PTV}}}$	Recommendation	-	-
	$D_{50\% \text{ Min/Max DVH}} = 60\text{Gy} + 14\text{Gy} \frac{SUV_{\text{median}}^{\text{mid PTV}}}{SUV_{\text{mean}}^{\text{mid PTV}}}$	Recommendation	-	-
Mid-treatment PTV FDG Li (i=1:N)	Mean Dose = $60\text{Gy} + 14\text{Gy} \frac{SUV_{\text{mean}}^{\text{mid PTV FDG Li}}}{SUV_{\text{mean}}^{\text{mid PTV}}}$	Recommendation	-	-
	Min Dose = $60\text{Gy} + 14\text{Gy} \frac{SUV_{\text{min}}^{\text{mid PTV FDG Li}}}{SUV_{\text{mean}}^{\text{mid PTV}}}$	Recommendation	-	-
	Max Dose = $60\text{Gy} + 14\text{Gy} \frac{SUV_{\text{max}}^{\text{mid PTV FDG Li}}}{SUV_{\text{mean}}^{\text{mid PTV}}}$	Recommendation	-	-
	$D_{50\% \text{ Min/Max DVH}} = 60\text{Gy} + 14\text{Gy} \frac{SUV_{\text{median}}^{\text{mid PTV FDG Li}}}{SUV_{\text{mean}}^{\text{mid PTV}}}$	Recommendation	-	-
Lung-CTV	Mean Dose < 20Gy	Objective	$\leq 22\text{Gy}$	$> 22\text{Gy}$
Lung-CTV	$V_{20\text{Gy}} < 37\%$	Objective	$\leq 40\%$	$> 40\%$
Lung-CTV	$V_{10\text{Gy}} < 50\%$	Objective	$\leq 55\%$	$> 55\%$
Lung-CTV	$V_{5\text{Gy}} < 60\%$	Objective	$\leq 70\%$	$> 70\%$
Perfused Lung-CTV	Mean Dose < 15 Gy	Objective	$\leq 20\text{Gy}$	$> 20\text{Gy}$
Lung-CTV PERF Li (i=1:N)	Mean Dose < $20\text{Gy} \frac{U_{\text{mean}}^{\text{Lung-GTV}}}{U_{\text{mean}}^{\text{Lung-GTV PERF Li}}}$	Recommendation	-	-
	Max Dose < $20\text{Gy} \frac{U_{\text{mean}}^{\text{Lung-GTV}}}{U_{\text{min}}^{\text{Lung-GTV PERF Li}}}$	Recommendation	-	-
	$D_{50\% \text{ Max DVH}} < 20\text{Gy} \frac{U_{\text{mean}}^{\text{Lung-GTV}}}{U_{\text{median}}^{\text{Lung-GTV PERF Li}}}$	Recommendation	-	-
Heart	$V_{60\text{Gy}} < 30\%$	Objective	$\leq 40\%$	$> 40\%$
Heart	$V_{45\text{Gy}} < 60\%$	Objective	$\leq 70\%$	$> 70\%$
Heart	$V_{40\text{Gy}} < 100\%$	Objective	-	100%
Heart	Mean Dose < 35Gy	Objective	$\leq 45\text{Gy}$	$> 45\text{Gy}$
Spinal Cord	$D_{0.03\text{cc}} < 50.5\text{Gy}$	Objective	-	$\geq 50.5\text{Gy}$
Esophagus	Mean Dose < 34Gy	Recommendation	-	-
Brachial Plexus	Max Dose < 66Gy	Recommendation	-	-

Table 2. FLARE RT adaptive planning objectives in select high local failure risk NSCLC patients classified as FDG PET non-responders. The composite dose of the functional avoidance RT plan administered in weeks 1-3 (15 fx) and the FLARE RT plan administered in weeks 4-6 (15 fx) would meet the following key objectives: (1) dose escalate residual FDG avid regions through linear dose redistribution at each FDG PET SUV-based dose level Li about 74 Gy mean dose to the mid-treatment PTV, (2) maintain perfused mean lung dose below 15 Gy, (3) redistribute each MAA perfusion SPECT uptake U-based dose level Li about 20 Gy mean dose to the anatomic lung. FLARE RT planning objectives will also include conventional dose-volume limits in accordance with standard clinical practice to heart, esophagus, spinal cord, etc. With

the exception of the mid-treatment PTV boost objectives, the same objectives will be applied to all remaining structures for patients selected to the functional lung avoidance arm (no dose escalation). All dosimetric objectives refer to radiation dose in units of Gray for photon therapy and Cobalt Gray Equivalent (CGE) for particle therapy.

